Clinicaltrials.gov ID: NCT03712410

Title: A Problem Solving Intervention for Hospice Caregivers

PI: [name]

Date of Document: December 20, 2022

Study Protocol and Data Analysis

Design

The study was designed as a randomized clinical trial with four groups. Hospice caregivers were randomly assigned to either to a group receiving standard hospice care with the addition of the PISCES intervention delivered face to face (Group 1) or a group receiving standard hospice care with the addition of the PISCES intervention delivered in a hybrid format (first session in person, remaining sessions via video) (Group 2) or a group receiving standard hospice care with the addition of the PISCES*plus* intervention delivered in a hybrid format (Group 3) or a group receiving standard hospice care with the addition of the PISCES*plus* intervention delivered entirely online (Group 4).

Setting and Participants

We partnered with Penn Homecare and Hospice Services. Penn Homecare and Hospice Services is an agency (part of the Penn Medicine system) that is Medicare and Medicaid-certified, accredited by the Joint Commission, licensed in the Commonwealth of Pennsylvania. It serves patients and families in Philadelphia, Chester, Delaware, Bucks and Montgomery counties mostly (total number of counties serves is 20) and is experiencing a growth over the years (20% increase in admissions over the past 5 years). The hospice component of the agency had a total number of 2,970 home admissions, an average daily census of 380 and an average length of service (LOS) of 68 days in 2016

Inclusion criteria for caregivers were the following:

- enrolled as a family/informal caregiver of a hospice patient
- 18 years or older
- with access to a standard phone line or Internet and computer access at home
- without functional hearing loss or with a hearing aid that allows the participant to conduct telephone conversations as assessed by the research staff (by questioning and observing the caregiver)
- no or only mild cognitive impairment—mental status will be assessed using the Short Portable Mental Status Questionnaire;¹ individuals with a score of less than seven (i.e., more than three errors) will be excluded, similar to other studies involving this instrument.
- speak and read English, with at least a 6th-grade education

Enrollment

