During the second visit (suggested timeline 11-13 days after hospice admission) the interventionist covers steps three and four of the ADAPT model. Step three encourages caregivers in being creative and generating alternative solutions. This step involves brainstorming possible solutions to the identified problem, encouraging caregivers to brainstorm many alternatives, defer judgment on these alternatives until a later stage of the intervention and think of a wide range of possible strategies (general) and tactics (more specific). Step four focuses on predicting the consequences and developing a solution plan. This step involves evaluating alternatives and choosing the one that is most likely to effectively solve the identified problem. Making effective decisions involves screening out obviously ineffective solutions, predicting possible consequences, evaluating solution outcomes, and identifying effective solutions/developing a solution plan.

The third visit (suggested timeline 16-18 days after hospice admission) focuses on step five, namely trying out the solution plan and determining if it works. The general goal is to systematically evaluate the solution that caregivers implemented as a result of the previous steps to determine if it was effective in solving (or improving) the identified problem.

Group 2: PISCES delivered in a hybrid format

In this group, participants received the PISCES intervention in three sessions; however, the first session was delivered face to face and the other two via video. The three intervention sessions

were scheduled with a suggested timeline between days 5 and 18 of the hospice admission as in Group 1.

The first session took place in person (suggested timeline 5-7 days after hospice admission) and included an explanation of the purpose of the visit/call, and confirmation of the three specific problems that the caregiver had selected from the concern list. During the first session, the interventionist worked on steps one and two of the ADAPT model of the PST, namely "Attitude" and "Defining the Problem and Setting Realistic Goals." After the first session where the in person encounter allowed for the establishment of rapport between the interventionist and the caregiver, the second session (suggested timeline 11-13 days after hospice admission) and the third session (suggested timeline 16-18 days after hospice admissions) were conducted via live videoconferencing.

Group 3: PISCESplus delivered in a hybrid format

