- time and travel associated with the installation and maintenance of videophones and addressing potential technical problems
- average salary paid by type of professional
- number and cost of hospital or emergency room visits for patients.

Other Measures

We assessed the quality of the video calls using a previously developed instrument for assessing the technical quality of a “virtual visit” in home care,^{xi} a video-based interaction between health care providers and patients or caregivers. This instrument is a form that will be filled out by the research staff after each video-session with a caregiver in Groups 2 and 3. The form includes identification of the caregiver, date, starting and ending time of the video-call. The main section of the form contains five items regarding the technical quality of the video-call. The first two items refer to the observations made by the research staff in regard the frequency of difficulties with audio and image by the research staff. The next two items address problems with video and sound at the caregiver’s end, as reported to the research staff during the video-call. The last item addresses possible disconnection(s) and their frequency of occurrence. This section allows for the definition of a score for the overall technical quality of each video-call. This instrument has been tested for reliability and validity and used to rate the technical quality of video-calls in home care settings.^{xii}

Data Analysis Plan

Data Analysis for Specific Aims 1 and 2

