The primary analyses focused on examining differences between treatment groups in terms of caregiver outcomes during the time of intervention. Changes in caregivers’ scores from baseline to post-treatment will be analyzed using analysis of covariance, with baseline score, site, and whether the caregiver’s patient has died, as covariates. Separate models were run for each outcome (caregiver quality of life, anxiety, depression, and problem-solving ability). For Specific Aim 1 (SA1) to assess the equivalence between PISCES F2F and PISCES in hybrid format, a confidence interval approach was used on the ANCOVA model, with a two-sided 5% level of significance. If the CI of the difference between the two groups falls within the pre-specified range of equivalence, the two interventions will be considered equivalent.^{xiii xiv} The range of equivalence is defined between $-\Delta$ and $+\Delta$. The clinically informed Δ s for the primary outcomes are: CQLI-R = 1.0; GAD-7 = 1.75; PHQ-9 = 2.0; PSI = 2.5, respectively. The analyses of equivalence will be on a per-protocol basis and will be supplemented by secondary sensitivity intent-to-treat analyses.⁵⁵

The analyses for Specific Aim 2 (SA2) focus on pair-wise comparisons between PISCES*plus* and the other treatment groups. A significance level of $\alpha=0.025$ for each comparison was used to account for the multiple (2) comparisons and assure an overall significance level of no more than 0.05 for each outcome. These analyses of superiority was on an intent-to-treat basis, using

multiple imputation to address missing data. ANCOVA and chi-square tests were used to determine whether attrition had an impact on sample composition. Specifically, analyses were computed on baseline demographic characteristics, as well as baseline outcome measures, to determine whether participants who completed all phases of data collection were initially different when compared with persons who did not complete the intervention. Data were analyzed using the Stata statistical package.

Data Analysis for Specific Aim 3

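### Specific Aim 1 equivalence is decided on a per-protocol set that the plan never defines, with intent-to-treat only a secondary check and no rule if the two disagree

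*Combined protocol and SAP*

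**What the plan says.** All of the following is in the combined protocol and SAP.

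- **Analysis set.** Data Analysis for Specific Aims 1 and 2: "The analyses of equivalence will be on a per-protocol basis and will be supplemented by secondary sensitivity intent-to-treat analyses".
- **Decision rule.** Same section: "If the CI of the difference between the two groups falls within the pre-specified range of equivalence, the two interventions will be considered equivalent". The interval comes from the ANCOVA "with a two-sided 5% level of significance", that is, a 95% interval. The margins are "CQLI-R = 1.0; GAD-7 = 1.75; PHQ-9 = 2.0; PSI = 2.5, respectively".
- **Missing data.** Same section: intent-to-treat with multiple imputation is specified for the Specific Aim 2 superiority comparisons. No method is given for the Specific Aim 1 intent-to-treat analysis.
- **Difference between the arms.** Group 1 has three home visits. In Group 2 "the first session was delivered face to face and the other two via video".
- **Technology.** Setting and Participants admits caregivers "with access to a standard phone line or Internet and computer access at home". Measures for Specific Aim 4 costs equipment and the "installation and maintenance of videophones and addressing potential technical problems". Other Measures describes a form that scores audio, image and disconnection problems after video sessions.
- **Timing of the outcome.** The paragraph before Treatment Fidelity places the post-intervention call after all three sessions are completed.

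Nowhere is there a minimum number of sessions, a rule on delivery mode, or a statement of how a failed or replaced video session affects membership of the per-protocol set.

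**The concern.** A per-protocol analysis compares caregivers selected after randomisation. It is safe only if the reasons for leaving the set are similar in the two arms or unrelated to outcome. Here neither can be judged in advance, because the set is undefined and the arms differ in just the feature (video) that could decide who is counted as treated per protocol. If Group 2 caregivers for whom video went badly were left out while comparable caregivers stayed in Group 1, a less effective format could appear equivalent.

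The planned safeguard is weak in two ways. First, the plan does not say that a failing intent-to-treat interval would stop a declaration of equivalence. Second, with the post-assessment tied to completing all sessions and no imputation named for this aim, the intent-to-treat run could rest on largely the same completers as the per-protocol run.

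**Working it through.** The documents give no sample size, power, dropout or per-protocol count for Specific Aim 1, so there is no planning figure to reproduce. The check asks how close the reported results lie to the margins, and how many exclusions from one arm would matter.

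**Inputs.** Mean change (SD) from Table 2, Comparison of 4 groups; n = 154 and 152 from Table 1, Participant characteristics. Follow-up n is not given.

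| Outcome | Group 1 | Group 2 | Margin |
|---|---|---|---|
| GAD-7 | -2.54 (4.25) | -1.49 (4.06) | 1.75 |
| PHQ-9 | -2.69 (4.29) | -1.56 (4.19) | 2.0 |
| CQLI-R | 1.14 (6.42) | 0.77 (4.82) | 1.0 |

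**Step 1: unadjusted 95% interval.** d = mean2 - mean1; SE = sqrt(SD1²/n1 + SD2²/n2); interval = d ± 1.96 × SE.

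- GAD-7: d = 1.05; SE = sqrt(4.25²/154 + 4.06²/152) = 0.475; 0.12 to 1.98.
- PHQ-9: d = 1.13; SE = sqrt(4.29²/154 + 4.19²/152) = 0.485; 0.18 to 2.08.
- CQLI-R: d = -0.37; SE = sqrt(6.42²/154 + 4.82²/152) = 0.648; -1.64 to 0.90.

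None lies inside its margin. GAD-7 exceeds it by 0.23 and PHQ-9 by 0.08, on the side where Group 2 improved less.

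**Step 2: exclude i caregivers from Group 2 only.** Assume that those excluded have mean change c, and leave Group 1 and both SDs unchanged. The new Group 2 mean is (152 × mean2 - i × c)/(152 - i), with n2 = 152 - i.

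With c = 0:

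- PHQ-9, i = 9 (5.9%): mean = -1.56 × 152/143 = -1.658; d = 1.032; SE = 0.492; upper limit 1.997, just inside 2.0. With i = 8 it is 2.006, outside.
- GAD-7, i = 24 (15.8%): mean = -1.49 × 152/128 = -1.769; d = 0.771; SE = 0.496; upper limit 1.743, inside 1.75. With i = 23 it is 1.755, outside.

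Other assumed values of c:

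| Excluded caregivers' mean change | PHQ-9 | GAD-7 |
|---|---|---|
| Half the Group 2 improvement | 20 (13.2%) | 47 (30.9%) |
| Zero | 9 (5.9%) | 24 (15.8%) |
| Worsened by as much as Group 2 improved | 5 (3.3%) | 12 (7.9%) |

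**Step 3: CQLI-R.** The half-width is 1.96 × 0.648 = 1.27, already wider than the margin of 1.0. Shifting the mean cannot bring the interval inside, and excluding caregivers only widens it.

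**Step 4: effect of baseline adjustment.** In Table 1 Group 1 starts higher by 6.69 - 5.74 = 0.95 on GAD-7 and by 7.54 - 6.6 = 0.94 on PHQ-9. If change falls by b points per baseline point, adjustment reduces d by about b × 0.95 or b × 0.94. With the SE held fixed, the intervals would come inside with no exclusions at b = 0.231/0.95 = 0.24 for GAD-7 and 0.080/0.94 = 0.09 for PHQ-9. The documents do not give b. The planned ANCOVA could therefore already place these two outcomes inside their margins.

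**Step 5: smaller follow-up n.** If 131 and 129 were followed up (about 15% loss, assumed), the intervals widen to 0.04 to 2.06 for GAD-7 and 0.10 to 2.16 for PHQ-9. More exclusions would then be needed than in step 2.

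PSI could not be checked because the tables give no PSI result.

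**The case against.** The strongest reply is that the arm-specific exit is an inference. A reader might conclude that Group 2 caregivers whose video failed, or who had only a phone line, were dropped from the per-protocol set. No text says so. The Group 2 section reports that the later sessions "were conducted via live videoconferencing", but attaches no exclusion to a failed or substituted session. Equipment price, depreciation and videophone installation are costed, so the programme may well have supplied equipment. That stands: bias is possible, not shown.

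Group 1 also has its own exits. Its description expects stressful events and frequent rescheduling of visits, and Group 2 avoids two of the home visits. That stands too, and leaves the net direction unknown.

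A reader might take Tables 2 and 3 as evidence of differential loss. Solving the pooled Traditional mean for Group 1's share gives (-2.04 + 1.49)/(-2.54 + 1.49) = 52.4% for GAD-7 (51.4% to 53.3% allowing for rounding), against 154/306 = 50.3% in Table 1. No cause is stated, these are follow-up records rather than per-protocol exclusions, and the CQLI-R range (48.7% to 54.1%) is compatible with no imbalance.

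Finally, per-protocol analysis is a conventional companion in equivalence trials, and an intent-to-treat analysis is already planned. That is a fair defence of running both. It does not defend letting an undefined set decide, with no stated consequence if the other analysis disagrees.

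**Conclusion.** The concern holds as a gap in specification. The set that decides Specific Aim 1 is undefined, the plan gives intent-to-treat no stated power to change the conclusion, and its missing-data method is not given.

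The size is enough to matter for two outcomes. Under the unadjusted illustration, removing about 6% of Group 2 (PHQ-9) or 16% (GAD-7), with zero mean change, would turn a failed equivalence criterion into a met one. Over the assumptions tried, the range is 3% to 13% and 8% to 31%. CQLI-R would not be moved inside by this route.

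These figures rest on Table 1 counts in place of follow-up counts, unchanged SDs, assumed outcomes for those excluded, and no baseline adjustment. They show that the GAD-7 and PHQ-9 intervals lie close to their margins. They do not show that the reported results are biased or that hybrid delivery is worse.

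**What to change.** 1. Declare equivalence for an outcome only if the per-protocol and the intent-to-treat intervals both lie within the margin.
2. Run the Specific Aim 1 intent-to-treat analysis on all caregivers randomised to Groups 1 and 2, analysed as randomised, with the same multiple imputation as Specific Aim 2.
3. State the per-protocol definition that was used, and report exclusions by arm and reason. This would show whether video problems removed anyone.

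A per-protocol rule that counts sessions whatever their mode is not recommended here: it would keep Group 2 caregivers switched to in-person sessions in the hybrid arm, make the arms more alike, and so favour equivalence.

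**Cost.** SAP wording, one imputed analysis and an exclusion table. The chance of declaring equivalence falls somewhat. Because the document already reports outcomes, the changed decision rule must be labelled post hoc and shown beside the result under the rule as written.

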Our cost analysis compared the three intervention groups with respect to total costs. Using the resource use and cost information, and the cost of client-specific hospitalizations and emergency department visits as described earlier, we estimated the total cost of care for each client. These data were used as the dependent variable in four pair wise regression analyses comparing the four groups with respect to total costs incurred over the study timeframe. Analysis of variance methods was employed. We also examined resource use, and compared this between groups. Specifically, we compared the number of after-hours calls and, and the number of hospitalizations and emergency department visits. As these outcome variables are each an event-count, each cannot be truly normal in distribution. Traditional regression methods assume a normally distributed outcome with constant variance. In contrast, count data are discrete and usually involve many observations with identical values and often highly right-skewed due to a few individuals with extreme event counts. We used both Poisson regression and the Zero-Inflated Poisson model for a comparison of the number of after-hour visits and calls. We also controlled for demographic covariates in these models. Direct and indirect costs for the hospice program were computed as the sum of implementation and operating costs. Intervention implementation costs included equipment costs (based on equipment price and depreciation), and staff training costs. Operating costs were measured by staff costs (wages and time) for delivery of the intervention (based on average wages and average time research staff took to do the intervention), and costs of home visits (frequency and duration) by all hospice staff as documented in the record review. Caregiver costs were based on overall informal care time (using income data gather upon admission), intervention time, any time lost from work, and out-of-pocket and travel expenditures related to caregiving as reported by the caregiver during the exit interview.

Table 1: Participant characteristics

Variable	Traditional Pisces		Online Pisces		
	Group 1 (n = 154)	Group 2 (n = 152)	Group 3 (n = 154)	Online (n = 63)	P-value
Caregiver Age [Mean (Std.)]	56.8 (12.7)	58.8 (12.8)	57.4 (12.2)	56.1 (17.2)	0.5664
Caregiver GAD 7 Score [Mean (Std.)]	6.69 (5.4)	5.74 (4.9)	6.32 (4.9)	5.85 (5.2)	0.4236
Caregiver PHQ-9 Score [Mean (Std.)]	7.54 (5.7)	6.6 (5.4)	6.99 (5.3)	6.78 (5.36)	0.5267

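### SA2's fixed 0.025 per comparison is valid, but a Holm step-down would keep the same 0.05 level per outcome and add some power for the second comparison (optional improvement)

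*Combined protocol and SAP*

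**What the plan says.** The paragraph on SA2 under Data Analysis for Specific Aims 1 and 2 says that the analyses "focus on pair-wise comparisons between PISCES*plus* and the other treatment groups". It fixes the level at 0.025 "for each comparison was used to account for the multiple (2) comparisons", so as to "assure an overall significance level of no more than 0.05 for each outcome". It describes no stepwise rule and does not say which two pairs are meant.

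The same section runs a separate model for each of four outcomes ("caregiver quality of life, anxiety, depression, and problem-solving ability"). The SA2 tests are ANCOVA, by intention to treat, with multiple imputation. The Design section states: "The study was designed as a randomized clinical trial with four groups". Two of the four, Groups 3 and 4, receive PISCESplus. The document gives no SA2 effect size, target power or planned sample size.

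**The concern.** The only purpose given for the 0.025 is to hold the overall level at 0.05 for each outcome. A fixed split is not the only way to do that. Once one of two comparisons is significant at 0.025, the closed-testing principle allows the other to be tested at 0.05, with familywise error still at most 0.05 under any dependence between the tests. This is Holm's procedure.

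At stake is the second comparison. If PISCESplus beat one comparator with p at or below 0.025 and the other with p of, say, 0.03, the written plan could claim only the first. Its own error guarantee would support both.

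**Working it through.** **1. The plan's own figure.** 0.025 + 0.025 = 0.05, which matches the stated bound. If the tests were independent, the error would be 1 − 0.975² = 0.0494. With a shared Group 3 and sizes 154/152/154 it is 0.046 by simulation. The split does what the plan says.

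**2. Inputs for the comparison of rules.**
- Group sizes 154, 152 and 154 for Groups 1 to 3, from the participant characteristics table. Follow-up numbers are not given, so these are upper bounds.
- SD of change 4.4 (assumption). Table 2 gives 4.25, 4.06 and 4.56 for GAD-7 in these groups.
- Group 3 against Groups 1 and 2 (assumption, because the pairs are not named).
- Two-sided tests (assumption). The wording "with a two-sided 5% level of significance" belongs to SA1; SA2 gives no sidedness.
- True differences of 1.0 to 2.0 GAD-7 points (assumption).

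**3. Rules.** Bonferroni rejects a comparison if its p ≤ 0.025. Holm also rejects it if its p ≤ 0.05 and the other p ≤ 0.025.

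**4. Power per comparison at 0.025, true difference 1.5.** SE = 4.4 × √(1/154 + 1/154) = 0.501, and 1.5/0.501 = 2.99. Power = Φ(2.99 − 2.24) = Φ(0.75) = 0.773. Simulation with 2,000,000 runs also gives 0.773.

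**5. Bonferroni to Holm, both effects real, simulated.**

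| True difference | At least one (both rules) | Group 3 vs Group 1 | Both comparisons |
|---|---|---|---|
| 1.0 | 56.3% | 40.2% → 44.8% | 24.0% → 33.1% |
| 1.25 | 76.0% | 60.0% → 65.4% | 43.7% → 54.6% |
| 1.5 | 89.5% | 77.3% → 82.1% | 64.8% → 74.5% |
| 1.75 | 96.5% | 89.5% → 92.6% | 82.2% → 88.6% |
| 2.0 | 99.1% | 96.0% → 97.5% | 92.7% → 95.9% |

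Per comparison the gain runs from 97.5 − 96.0 = 1.5 points to 65.4 − 60.0 = 5.4 points. For both it runs from 95.9 − 92.7 = 3.2 to 54.6 − 43.7 = 10.9 points. It is largest at middling power. Group 3 vs Group 2 behaves almost identically (77.0% → 81.9% at 1.5).

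**6. Only one effect real (1.5 points).** Power for that comparison goes from 77.0% to 77.2%.

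**7. Error.** With no true effects, the chance of any rejection is 0.046 under either rule.

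**8. Dependence on the number of comparisons.** If Groups 3 and 4 were each compared with Groups 1 and 2, there would be four tests. At 0.025 each the bound is 4 × 0.025 = 0.10 (simulated 0.084), and Holm would have to start at 0.05/4 = 0.0125. If Group 3 were compared with all three other groups, the bound is 3 × 0.025 = 0.075 (simulated 0.067).

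**9. Would it change anything reported?** These are approximate z-tests on the unadjusted changes in Table 2, with the participant-table group sizes. They show the smallest p for Group 3 against Group 1 or 2.
- GAD-7, vs Group 2: difference −2.27 − (−1.49) = −0.78, SE √(4.56²/154 + 4.06²/152) = 0.493, z = −1.58, p ≈ 0.11.
- PHQ-9, vs Group 1: difference 0.82, SE 0.506, p ≈ 0.10, in favour of Group 1.
- CQLI-R, vs Group 1: difference −0.87, SE 0.776, p ≈ 0.26.

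None reaches 0.025, so Holm would stop at its first step. These are not the planned imputed ANCOVAs, and no PSI result is reported.

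**The case against.** The strongest defence is that nothing is broken. The split is valid, and the document states no power target that it misses. It also has practical merits: simple 97.5% simultaneous intervals that match the tests, and a verdict on each comparison that does not depend on the other. All of this stands, and it is why the point is optional.

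A reader might go further and infer that the fixed split gives away power for nothing. The figures do not support that. The chance of a first significant comparison is the same under both rules, the gain almost vanishes when only one effect is real, and Holm has a cost in its intervals. A reader might also infer that the advantage over the plan's 0.025 holds for any number of comparisons. It does not. Holm beats Bonferroni for the same family, but with four comparisons its first step, at 0.0125, is stricter than the level now written. Which pairs form the family in a four-group trial with two PISCESplus arms is the more material question and has to be settled first.

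The size of the gain is also open to challenge. The 1.0 to 2.0 point effects are assumed. At 1.75, the plan's own GAD-7 equivalence margin, the gain per comparison is about 3 points. The SD of 4.4 is for unadjusted change rather than baseline-adjusted scores, and it does not represent CQLI-R (4.82 to 7.17). This limits the precision of the figures. It does not affect the result that Holm never rejects less when there are two comparisons.

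**Conclusion.** The point holds as an efficiency remark. With exactly two SA2 comparisons per outcome, Holm keeps the 0.05 familywise level and improves the chance of establishing the second comparison when both effects are real. The size in step 5 rests on two-sided tests of Group 3 against Groups 1 and 2, the assumed SD and effects, and no loss to follow-up. Neither rule adjusts across the four outcomes, because the plan controls error within each outcome only.

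This is not an error in the plan. The document is dated December 20, 2022 and already contains group results, so a more permissive rejection rule adopted now would be post hoc. On the approximate figures it would probably alter no reported conclusion. Its practical value is for a re-analysis or a successor protocol.

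**What to change.** 1. Name the two SA2 comparisons.
2. Replace the fixed level with: for each outcome, test the smaller of the two p-values at 0.025 and, only if it is significant, the other at 0.05, using the same ANCOVA with multiple imputation. If more than two comparisons are intended, start at 0.05/m, where m is their number, and step down through 0.05/(m − 1) and so on, stopping at the first non-significant result.
3. With two comparisons, report 97.5% intervals beside the Holm decisions. State that a second comparison won at a p between 0.025 and 0.05 will have a 97.5% interval that includes zero, and that the decision follows Holm.
4. If the rule is applied to this trial's data, label it post hoc and show the result at the fixed 0.025 as well.

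The cost is a sentence or two of SAP text, with no new data or participants, and a less simple match between intervals and decisions.
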